IT Baclofen Drug Distribution Pilot Study: Proposal to Medtronic

Goal:

While ITB therapy is commonly recommended for treatment of severe spasticity due to a variety of diseases, the location of optimal drug (baclofen) delivery has not been defined in a controlled study. Furthermore, the cost of pharmacological management in these patients is significant, and optimal location for drug delivery through an implantable drug pump may have significant impact on the cost burden of maintenance refills. It is the goal of this pilot study to determine whether there is a significant therapeutic advantage to place the ITB catheter within the cervical, thoracic or lumbar region of the spine. It is also a goal of this pilot study to determine whether the origin of spasticity influences the effect of Lioresal Intrathecal (baclofen injection) on ITB catheters located in the cervical, thoracic or lumbar regions of the spine. We propose to study the impact of catheter location on the reduction in spasticity within a group of patients who are scheduled for ITB trial. Furthermore, we intend to enroll patients whose spasticity originates from two different mechanisms (SCI causing spastic paraplegia vs. cerebral palsy causing spastic spasticity of spinal and cerebral origin). In studying the impact of catheter location among patients with spinal versus cerebral origin of spasticity, the disease origin may also have a significant impact on baclofen dosing relative to the placement of the catheter.

In addition, the pharmacokinetic half-life and the variability of intrathecal baclofen is poorly understood as data is limited. In order to provide initial data regarding CSF baclofen washout, samples of spinal fluid obtained just prior to- and following IT baclofen administration will be obtained for delayed analysis. The results of these pharmacological analysis may refine the understanding of how quickly baclofen is distributed from a given catheter location, and whether it is affected by catheter location or disease origin. Since multiple catheter locations will be studied within a given patient, it also affords the opportunity to sample small amounts of CSF at key anatomical sites along the spinal axis as an independent secondary study protocol.

Hypotheses:

- H₀₁: There is no significant ($p > 0.05$) difference in clinical spasticity (as measured by using the Modified Ashworth Spasm Rating Score) when the same amount of baclofen is delivered (50 μ g) to the cervical, thoracic, or lumbar area on separate days.
- H₀₂: There is no significant ($p > 0.05$) difference in the response to Lioresal Intrathecal (baclofen injection) between patients with spinal versus cerebral origin of spasticity relative to catheter tip placement.

Specific Aims:

1. Measure the degree of spasticity based on the Modified Ashworth Scale for Grading Spasticity in patients undergoing daily, single ITB bolus injections through an intrathecal catheter located in the mid-cervical (C4), mid-thoracic (T3), thoraco-lumbar (T10) and upper lumbar (L2) regions.
2. Measure the Spasm Rating of patients undergoing daily, single ITB bolus injections through an intrathecal catheter located in the mid-cervical (C4), mid-thoracic (T3), thoraco-lumbar (T10) and upper lumbar (L2) regions.

3. Sample CSF at each of the catheter tip locations just prior to ITB injection. Sample CSF at 1, 5, 10, 20, 60 min following ITB administration.
4. Each subject will receive prophylactic antibiotics for the duration of the IT catheter placement.

Methods:

Subjects who have spasticity and have consented for a trial of ITB therapy as part of a normal therapeutic evaluation, will be asked to enroll in this study. As a pilot study, we are interested in observing significant changes ($p < 0.05$) in either Ashworth Rigidity or Spasm scores related to catheter tip location along the spinal axis. Each subject will serve as their own control and will be assessed by the same rater throughout the study. The subjects will initially undergo temporary implantation of an intrathecal catheter placed under sedation or light anesthesia with fluoroscopic guidance. This will be done by the neurosurgeon with the intent of positioning the catheter initially in the mid-cervical region (C4) of the spine. The following day, after sedation / anesthetic effects are worn off, the subject will undergo a spasticity evaluation in the morning prior to ITB injection (See Tables 2 and 3 regarding Modified Ashworth and Spasm rating scores). Then a 50 microgram (μg) dose of IT baclofen will be injected into the CSF through the catheter. Samples of CSF (3cc) will be withdrawn from the IT catheter just prior to injection and at 10, 30, 60, 120, and 360 min following the ITB injection. The rater (Nurse Practitioner) will perform an Ashworth and Spasm rating exam on the subject at 2, 4, and 6 hours following the ITB injection. Each subject will be allowed to recover and observed overnight in the Clinical Research Center (CRC) at Vanderbilt University.

The following morning, each subject will be brought to the radiology department fluoroscopy room and the IT catheter withdrawn to the next lower level being studied – viz. T3, T10, or L2. Catheter position prior to- and after repositioning will be documented on digital radiograph. The subjects will then be returned to the CRC area and dosed with IT baclofen (50 micrograms IT baclofen). The same protocol for assessing spasticity (Ashworth score) and spasms (Spasm rating) will be performed that day associated with the new catheter position. In other words, a spasticity assessment will be performed just prior to injection, and at 2 hour intervals following injection up to 6 hours after injection. Likewise, a CSF sample will be withdrawn just prior to injection, and at logarithmic intervals up to 6 hours following injection. Each CSF sample will be no more than 3 cc and must represent a clean sample of CSF from the subject.

At the end of the fifth day of study, the IT catheter will be withdrawn and a stitch placed over the hole in the skin. The subject will be allowed to stay overnight for observation and then released the following morning. Implantation of the ITB pump will be determined as usual by the implanting neurosurgeon and his staff (*note: The decision as to whether the subject or the clinical team decides to implant an ITB pump is outside the scope of this project, and would be considered part of their routine medical care following the trial of ITB*).

Selection of subjects. We will attempt to enroll ten subjects for each disease category by the end of two years. A total of 20 subjects would be enrolled to complete this study. We wish to enroll subjects with similar mechanisms of spasticity for each disease category. Our initial disease categories will involve subjects who have spasticity from very different mechanisms to determine if ITB dosing is significantly different due to origin of spasticity. One group of subjects would have spasticity due to spinal cord injury and are paraplegic, thereby recognizing that their spasticity originates from the lower half of the spinal cord in general. Another group of subjects would have spasticity due to cerebral palsy and are

quadriparetic, thereby recognizing that their spasticity originates from loss of upper motor neurons as a result of cerebral disease (typically associated with a perinatal infarct). Other disease categories, such as cervical spine SCI, stroke, hereditary spastic paraparesis, multiple sclerosis, can be considered in the future if a significant difference ($p < 0.05$ on ANOVA analysis) exists between the two broad categories represented in this pilot study.

There may be reasons why subjects may not be able to complete the study. Some foreseeable reasons include:

- Intradural blockage that prevents advancing the IT catheter to the level of C4, verified by a total MRI of the spine (Cervical, Thoracic, and Lumbar levels), without contrast injection, sagittal views only.
- Significant left over effect of the previous day's administration of IT baclofen thereby prevent a detectable change in spasticity in subsequent injections
- Allergic reaction to IT baclofen
- Withdrawal of the subject from the study
- IT catheter malfunction
- Significant headache from CSF withdrawal
- CSF leak that is intolerable (headache or otherwise) from the IT catheter entry site

Results Anticipated:

The data will be collected according to the following schedule per patient.

Table 1. Study variables and the timing of data collection. Each table is for a specific catheter location within a given patient. This table, for example, would be filled out 4 times corresponding to the four different catheter locations studied each day.

Time	Catheter Location	Modified Ashworth Score	Spasm Score	CSF Sample
Baseline	C4, T3, T10, L2	0-4	0-4	3cc
Injection (50µg)	-	-	-	-
1 min	-	-	-	3cc
2 min	-	-	-	3cc
10 min	-	-	-	3cc
20 min	-	-	-	3cc
60 min	-	-	-	3cc
2 hours (120min)	-	0-4	0-4	-
4 hours (240 min)	-	0-4	0-4	-
6 hours (360 min)	-	0-4	0-4	-
Total				18 cc / day

Table 2. Modified Ashworth Scale for Grading Spasticity

Grade	Clinical Rating of Tone
0	No increase in tone
1	Slight increase in muscle tone, manifested by a catch and release, or by minimal resistance at the end of the range of motion when the affected

	part(s) is moved in flexion or extension
1+	Slight increase in muscle tone, manifested by a catch, followed by minimal resistance throughout the remainder (less than half) of the ROM
2	More marked increase in muscle tone through most of the ROM, but affected part(s) easily moved
3	Considerable increase in muscle tone, passive movement difficult
4	Affected part(s) rigid in flexion or extension

[figure not shown]
Table 3. Penn Spasm Frequency Scale

Spasm Score	Spasm Frequency
0	No spasms
1	Mild spasms induced by stimulation
2	Infrequent full spasms occurring less than once per hour
3	Spasms occurring more than once per hour
4	Spasms occurring more than 10 times per hour

Spasm Severity	Severity Rating
1	Mild
2	Moderate
3	Severe

For a given subject, the data will be analyzed for the following effects:

1. What was the effect of identical baclofen doses (50µg) administered at different spinal levels within each subject on rigidity? (expect reduction in score over 4-6 hours with possible return towards baseline at 6-10 hours)
2. What was the effect of identical baclofen doses (50µg) administered at different spinal levels within each subject on spasms? (expect reduction in score over 4-6 with possible return towards baseline at 6-10 hours)
3. Is there a significant difference in location of the catheter on the maximum reduction in either spasticity or spasm scores? (expect this to show as the largest “dip” in scores on 3D graph)
4. Is there a “washout” effect from day to day? (if so, expect the baseline scores to be lower each day) If present, this would suggest that the daily dosing is too high.

[figure not shown]

For each group (SCI vs CP), the data will be analyzed as follows:

1. What catheter location caused the greatest change in spasticity scores? (the location of the catheter – C4, T3, T10 or L2 – would be noted and averaged among the ten subjects). Expect that

SCI group would favor greater change when catheter is located at T10 or L2. Expect that CP group might not show a significant difference in catheter location.

2. What catheter location caused the greatest change in spasm scores? (the location of the catheter – C4, T3, T10 or L2 – would be noted and averaged among the ten subjects) Expect that SCI group would favor greater change when the catheter is located at T10 or L2. Expect that the CP group would not have much spasm change based on catheter location.

Parameter	SCI Paraplegic (n=10)	CP Quadriparetic (n=10)
Greatest change in Ashworth Score vs Location	? ANOVA	? ANOVA
Greatest change in Spasm Rating vs Location	? ANOVA	? ANOVA
Difference in Ashworth Score between days (assess washout effect)		

Subject Recruitment and Length of Study:

We expected to be able to recruit 20 patients for this study within two years. The subjects would be solely recruited and managed through the Adult Neurosurgery practice at Vanderbilt. Patients would be approached for enrollment after first choosing to undergo an ITB trial for the treatment of their spasticity.

Procedure/Activity	Frequency
Patient consent	Clinic visit 1 1
MRI Total Spine without contrast	Outpatient Radiology 1
Implantation of intrathecal catheter under light sedation and fluoroscopy guidance to C4	Inpatient MCE Day 1 1 Transfer to CRC after wake-up from MCE procedure (CRC Day 1)
Baclofen Injection (50µg)	Inpatient CRC Day 2
Modified Ashworth Rigidity testing and Spasm rating	Inpatient CRC Day 2 at 2, 4, and 6 hours following injection
CSF Specimen 3cc	Inpatient CRC Day 2 10 min, 30 min, 60 min, 120 min, 360 min
Repositioning of intrathecal catheter to next lower level or T3 under fluoroscopy	Inpatient Radiology Day 3 1 (for this day)
Baclofen Injection (50µg)	Inpatient, CRC, Day 3
Modified Ashworth Rigidity testing and Spasm rating	Inpatient, CRC Day 3 at 2, 4, and 6 hours following injection
CSF Specimen 3cc	Inpatient CRC Day 3 10 min, 30 min, 60 min, 120 min, 360 min
Repositioning of intrathecal catheter to next lower level or T10 under fluoroscopy	Inpatient Radiology Day 4 1 (for this day)
Baclofen Injection (50µg)	Inpatient CRC Day 4
Modified Ashworth Rigidity testing and Spasm rating	Inpatient CRC Day 4 at 2, 4, and 6 hours following injection,
CSF Specimen 3cc	Inpatient CRC Day 4 10 min, 30 min, 60 min, 120 min, 360 min

Repositioning of intrathecal catheter to next lower level or L2 under fluoroscopy	Inpatient Radiology Day 5	1 (for this day)
Baclofen Injection (50 μ g)	Inpatient CRC Day 5	
Modified Ashworth Rigidity testing and Spasm rating	Inpatient CRC Day 5 at 2, 4, and 6 hours following injection	
CSF Specimen 3cc	Inpatient CRC Day 5 10 min, 30 min, 60 min, 120 min, 360 min	
Catheter withdrawal	Inpatient CRC, Day 5	
Discharge	Inpatient, CRC, Day 6

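### H01 and H02 are defined by p > 0.05 and SCI and CP are tabled as separate ANOVAs, so with ten per group a non-significant result is liable to be read as no effect

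*Combined protocol and SAP*

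**What the plan says.** - **Hypotheses.** H01 is "There is no significant ($p > 0.05$) difference in clinical spasticity" when the same amount of baclofen is delivered at different levels. H02 is "There is no significant ($p > 0.05$) difference in the response to Lioresal Intrathecal (baclofen injection) between patients with spinal versus cerebral origin of spasticity"; that comparison is tied to where the tip of the catheter lies.
- **Methods.** The aim is put in the usual direction: "we are interested in observing significant changes ($p < 0.05$) in either Ashworth Rigidity or Spasm scores related to catheter tip location". The design is within-subject: "Each subject will serve as their own control and will be assessed by the same rater throughout the study".
- **Selection of subjects.** "We will attempt to enroll ten subjects for each disease category by the end of two years", which makes 20 in all. Other disease categories "can be considered in the future if a significant difference" at p < 0.05 on ANOVA exists between the two categories.
- **Results Anticipated, group analyses.** For SCI, a larger change is expected at T10 or L2. For CP: "Expect that CP group might not show a significant difference in catheter location". The table beneath has one column per group, each marked ANOVA with a question mark.
- **Not given.** There is no SD, effect size, power, minimum important difference, confidence interval or interaction test, and no statement of how a non-significant result will be interpreted.

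**The concern.** A null hypothesis should be a statement about the true effect. H01 and H02 are statements about the sample p-value, so failing to reach significance makes each of them hold as written, however large the true difference. Three other features push the same way:

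- the anticipated CP result is itself a non-significant one;
- the tabled analysis tests location within SCI and within CP, and nothing in it compares the two location effects, although that comparison is what H02 is about;
- the next step is tied to p < 0.05 between SCI and CP.

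At stake are the study's main message (that SCI responds best at T10 or L2 while CP shows no preference) and the choice of which diseases to study next. Either could rest on an inconclusive result taken as a negative one, or on a contrast between one significant and one non-significant p-value.

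**Working it through.** **Inputs from the documents:** n = 10 per group, 20 in total; four levels within subject; alpha 0.05. **Assumptions:** two-sided testing, standardised effects of 0.5 to 1.0 SD, within-subject correlation ρ of 0.3 to 0.7, sphericity, and scores treated as continuous. The stated sample size cannot be reproduced because no effect size, SD or power stands behind it. What can be computed is how n = 10 per group performs.

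**1. Two levels within one group (paired t, n = 10, 9 df).** Unit: SD of the paired difference.
- 95% CI half-width = t(0.975, 9)/√10 = 0.72 SD.
- Power from the noncentral t with noncentrality d√10: 29% at 0.5, 62% at 0.8, 80% at 1.0.

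**2. SCI versus CP, main-effect comparison (two-sample t, 10 v 10, 18 df).**
- 95% CI half-width = t(0.975, 18) × √(2/10) = 0.94 SD.
- Power with noncentrality d√(10/2): 19% at 0.5, 40% at 0.8, 56% at 1.0. So a true 1.0 SD difference misses p < 0.05 in 100 − 56 = 44% of studies.
- 80% power needs 1.32 SD, or 1.51 SD if 8 per group complete (assumed).

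**3. Location effect and interaction (noncentral F).** Assumed pattern: C4 = T3, with T10 and L2 both shifted by R = 0.5 SD of the score at a level.
- Location within one group: λ = nR²/(1 − ρ) = 10 × 0.25/(1 − ρ), on 3 and 27 df.
- Group-by-location, shift in SCI only: the squared interaction terms sum to R²/2, so λ = 10 × 0.125/(1 − ρ), on 3 and 54 df.

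| ρ | λ, one group | Power, one group | λ, interaction | Power, interaction (H02) |
|---|---|---|---|---|
| 0.3 | 3.57 | 28% | 1.79 | 17% |
| 0.5 | 5.00 | 39% | 2.50 | 22% |
| 0.7 | 8.33 | 60% | 4.17 | 35% |

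A real 0.5 SD effect is therefore non-significant in about 40–72% of studies within one group, and in about 65–83% for H02.

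**4. Same effect in both groups.** If SCI and CP share the 0.5 SD location effect, the chance that SCI is significant and CP is not is p(1 − p), where p is the one-group power:
- ρ = 0.3: 0.283 × 0.717 = 0.20
- ρ = 0.5: 0.386 × 0.614 = 0.24
- ρ = 0.7: 0.604 × 0.396 = 0.24

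The pattern that the plan anticipates thus appears 20–24% of the time when origin makes no difference.

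**5. H01 pooled over all 20 (paired t, 19 df).** Half-width = t(0.975, 19)/√20 = 0.47 SD. Power is 56% at 0.5 SD, and 80% power needs about 0.66 SD.

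**6. In points on the 0–4 scores.** If the relevant SD were anywhere from 0.5 to 1.5 points (assumed), the SCI–CP half-width would be 0.94 × 0.5 = 0.47 to 0.94 × 1.5 = 1.41 points.

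**The case against.** A reader might infer that the sponsor has committed to concluding no effect from p > 0.05. The documents do not say so. The CP sentence is a hedged prediction, the matching expectation for spasms is about size rather than significance, and predicting a null is not the same as planning to infer one.

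A reader might also infer that other diseases will be studied only if p < 0.05. The text is permissive: it says they can be considered, it concerns possible later work, and leaving a pilot unextended is not a claim that origin is irrelevant. Both objections stand.

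It is also fair that the p > 0.05 inside the hypotheses may be no more than a clumsy way of giving alpha, given the ordinary wording in Methods. And ten per group is not the sample for H01, which does not split by disease and can use all 20 subjects. That stands too, and step 5 shows the gain.

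Last, every effect in SD units is assumed, and ANOVA on ordinal 0–4 scores is an approximation. The two-sample figure fits only a main-effect reading of the p < 0.05 condition. H02 itself is an interaction, and its power is in step 3.

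None of this supplies what is missing: a direct comparison of location effects between SCI and CP, an interval, or a rule for a non-significant result. Nor does the pilot label help, since a small study is where a significance threshold tells least and an estimate with its interval tells most.

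**Conclusion.** The concern holds as a risk of misreading that the wording and the tabled analysis invite, and not as a stated intention to conclude no effect. It bears on H02, the group-specific ANOVAs and the p < 0.05 condition for later disease categories. It bears less on H01.

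Under the stated assumptions, a 0.5 SD location effect has 28–60% power within one group and 17–35% as an SCI-only interaction. A 1.0 SD main-effect difference between SCI and CP has 56%. Identical 0.5 SD effects in both groups would look different on separate tests about one time in four or five. The exact percentages depend on SDs and correlations that the documents do not give. What does not depend on them is that a non-significant result with ten per group leaves an interval of roughly ±0.7 SD of the paired difference for two levels within one group, and ±0.9 SD between groups.

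**What to change.** 1. State H01 as equal mean change from baseline across the four levels, and H02 as equal level differences in SCI and CP.
2. Test H02 by the group-by-location interaction in one repeated-measures model on all 20 subjects, instead of comparing two within-group p-values.
3. Report each level difference and each SCI–CP difference with a 95% CI.
4. State that p > 0.05 is inconclusive and is not evidence that location or origin does not matter.
5. Inform the choice of further disease categories by the estimated SCI–CP difference and its CI, rather than by p < 0.05 alone.

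**Cost.** No extra subjects, procedures or visits, and a little more analysis. Most expected statements of no difference in CP would become inconclusive.

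The sponsor should not expect to replace them with a claim of equivalence. With a true difference of zero, two one-sided tests at n = 10 paired have about 7% power for a 0.5 SD margin, 52% for 0.8 SD and 79% for 1.0 SD. These margins are assumed, since the documents give none.

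**What this does not repair.** Methods and the procedure schedule fix the catheter order as C4, T3, T10, L2, so level differences stay confounded with day and with carryover, which the plan itself foresees. A narrow CI would therefore not by itself establish that there is no location preference, and the report should say so.

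### The post-dose CSF sampling times conflict: Aim 3 and Table 1 stop at 60 min, Methods and the procedure table run to 360 min, and nothing says which governs

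*Combined protocol and SAP*

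**What the plan says.** Post-dose CSF times appear in four places.

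- **Specific Aims, item 3:** "Sample CSF at 1, 5, 10, 20, 60 min following ITB administration", after a pre-dose sample.
- **Results Anticipated, Table 1:** 3 cc at baseline and at 1, 2, 10, 20 and 60 min, with a dash in the CSF column at 2, 4 and 6 hours. The table is introduced by "The data will be collected according to the following schedule per patient", and its caption adds "This table, for example, would be filled out 4 times corresponding to the four different catheter locations studied each day".
- **Methods, first catheter position:** CSF is taken "just prior to injection and at 10, 30, 60, 120, and 360 min following the ITB injection". For the later positions, Methods gives a pre-dose sample and then sampling "at logarithmic intervals up to 6 hours following injection", with no times listed.
- **Procedure/Activity table, Days 2 to 5:** "10 min, 30 min, 60 min, 120 min, 360 min" on each dosing day.

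The Goal section says that the half-life of intrathecal baclofen is poorly understood and gives initial washout data as the reason for sampling. It adds that the results may refine the understanding of how quickly the drug is distributed. It also describes the CSF sampling along the spinal axis as a secondary study.

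**The concern.** The schedules cannot all be followed as written, and no section is given precedence. Table 1 reads as the form to be completed at each catheter location, so it could well be what bedside staff use. If so, the two samples that Methods places at 120 and 360 min are never drawn, and they cannot be obtained afterwards. Those are the times that bear most directly on washout.

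If staff follow Methods or the procedure table, nothing is drawn between injection and 10 min. If different subjects or days are handled under the 60-min and 360-min versions, only the 10-min and 60-min concentrations can be compared across catheter locations and between the SCI and CP groups.

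**Working it through.** **1. The plan's own figure.** Table 1 totals 18 cc per day. One pre-dose plus five post-dose samples at 3 cc gives (1 + 5) × 3 = 18 cc, so the figure reproduces. It is a maximum, since Methods says "Each CSF sample will be no more than 3 cc". Aim 3 and Methods also have one pre-dose and five post-dose samples, so the total cannot show which schedule is meant.

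**2. The times side by side (minutes after injection).**

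| Source | Times | Last |
|---|---|---|
| Aim 3 | 1, 5, 10, 20, 60 | 60 |
| Table 1 | 1, 2, 10, 20, 60 | 60 |
| Methods, first position | 10, 30, 60, 120, 360 | 360 |
| Procedure table, Days 2–5 | 10, 30, 60, 120, 360 | 360 |

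Aim 3 and Table 1 share four of five times and differ only at 5 versus 2 min. Each shares only 10 and 60 min with Methods.

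**3. Could the lists be complementary?** Their union is 1, 2, 5, 10, 20, 30, 60, 120 and 360 min: nine post-dose samples plus one pre-dose. At 3 cc each that is 10 × 3 = 30 cc, against the stated 18 cc. They are alternatives.

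**4. Size of the loss (illustration only).** The documents give no pharmacokinetic model, half-life or assay error. Assume mono-exponential decline and compare the standard error (SE) of the elimination rate k under each 60-min schedule with that under 10–360 min.

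*Constant CV.* The log concentration is linear in time and SE(k) is proportional to 1/√Sxx, where Sxx = Σ(t − t̄)².

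- Aim 3: Sxx = 2282.8. Table 1: 2375.2. Methods: 81,320 (mean 116 min).
- Ratios: √(81,320/2282.8) = 5.97 for Aim 3 and √(81,320/2375.2) = 5.85 for Table 1.
- The 360-min sample alone supplies (360 − 116)² = 59,536, which is 73% of 81,320.
- If that sample is not quantifiable, 10, 30, 60 and 120 min remain, with Sxx = 6900. The ratios become √(6900/2282.8) = 1.74 and √(6900/2375.2) = 1.70.

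*Additive error.* The model is A·exp(−kt), and SE(k) comes from the inverse of J′J with J = [C, −tC].

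| Assumed half-life | SE ratio, Aim 3 | SE ratio, Table 1 | Decline completed by 60 min | 360-min level as share of 10-min level |
|---|---|---|---|---|
| 30 min | 0.89 | 0.86 | 75% | 0.03% |
| 1 h | 1.17 | 1.14 | 50% | 1.8% |
| 3 h | 2.47 | 2.42 | 21% | 26% |
| 5 h | 3.46 | 3.39 | 13% | 45% |

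The last two columns are 1 − 2^(−60/half-life) and 2^(−350/half-life), with the half-life in minutes.

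**5. Procedure table against the other sections.** On each dosing day it lists five CSF samples (5 × 3 = 15 cc) and ratings at 2, 4 and 6 hours. It does not list the pre-dose CSF sample, which is in Aim 3, Methods and Table 1. Nor does it list the baseline rating, which is in the Table 1 baseline row and in Methods: "the subject will undergo a spasticity evaluation in the morning prior to ITB injection".

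**The case against.** The strongest reply is that the operational text is consistent. Methods and all four dosing days of the procedure table agree, and the up-to-6-hours wording for later positions fits them. On that view Aim 3 and Table 1 are leftovers that staff would not follow. This lowers the risk for Aim 3. It does not remove it for Table 1, which is presented as the data-collection schedule and has no CSF entry after 60 min.

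A second objection is that the SE ratios prove little. They range from no loss to a large loss, they belong to an estimator the plan never specifies, and they put samples taken 1 to 5 min after a bolus on the same line as elimination. This is correct. The contradiction is established by comparing the times, and the ratios only illustrate what may be at stake.

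Some stronger readings are tempting but are not supported:

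- *Three equally serious conflicts.* The 5 versus 2 min difference is minor and may be a slip. In substance there are two families, ending at 60 or at 360 min.
- *The plan leaves open whether washout or early distribution is the aim.* The Goal section names washout as the purpose and mentions distribution only as something the results may refine.
- *The loss matters only if the half-life is long.* That pattern appears under additive error. The constant-CV ratios contain no half-life, and the case most plausible at short half-lives (360-min sample unquantifiable) still gives about 1.7.
- *The procedure table deliberately covers only events after injection.* It also lists consent, MRI, catheter placement and repositioning, so this does not explain the missing pre-dose items.

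**Conclusion.** The point holds and should be fixed. The plan gives CSF schedules ending at 60 min in two places and at 360 min in two others, shares only 10 and 60 min across all of them, and names none as governing. This rests on the text alone.

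The consequence for washout depends on assumptions. The ratio of SEs for the elimination rate, 60-min schedules against 10–360 min, is 5.9 to 6.0 under constant CV. It is about 1.7 under constant CV if the 360-min sample cannot be quantified. Under additive error it runs from about 0.9 (30-min half-life) to about 3.5 (5-h half-life). None of these can be picked as the expected value from the documents.

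A reader might infer that the trial's main comparisons are compromised. They are not. H01 and H02 concern clinical response, and the day-to-day carry-over check uses baseline spasticity scores. None of these uses CSF data. The damage is confined to the secondary pharmacokinetic component, where it would be irreversible.

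**What to change.** Reconcile Aim 3, Methods, Table 1 and the procedure table to one list of CSF times, used at every catheter location. Replace the reference to logarithmic intervals with that list.

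For the stated washout purpose, the times to 360 min already in Methods and the procedure table are suitable, so Aim 3 and the CSF column of Table 1 would be edited to match. The cost is losing the samples before 10 min (1 and 5 min in Aim 3, 1 and 2 min in Table 1) and the 20-min sample, in exchange for 30, 120 and 360 min. If the sponsor prefers the early times, it should say so, settle 2 versus 5 min, edit Methods and the procedure table, and accept that there will be no CSF data after 60 min.

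As a completeness edit, add the pre-dose CSF sample and the baseline rating to each dosing day of the procedure table.

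Both choices are wording changes. The count stays at one pre-dose plus five post-dose samples, with the same maximum of 18 cc per day.

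### H01 names an undefined merged outcome, and either of two scores may count at an unadjusted p < 0.05, so the chance of a false positive can reach about 10% per group and about 19% over the four ANOVAs

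*Combined protocol and SAP*

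**What the plan says.** - **Hypotheses, H01.** The null hypothesis of no location effect is set at p 0.05, with clinical spasticity "as measured by using the Modified Ashworth Spasm Rating Score".
- **Results Anticipated, Tables 2 and 3.** The protocol defines two scales, the Modified Ashworth Scale and the Penn spasm scale. Specific Aims 1 and 2 measure them separately. No scale under the merged name in H01 is defined.
- **Methods, first paragraph.** As a pilot, the study is interested in changes that reach p < 0.05 "in either Ashworth Rigidity or Spasm scores related to catheter tip location along the spinal axis".
- **Per-subject analysis question 3.** "Is there a significant difference in location of the catheter on the maximum reduction in either spasticity or spasm scores".
- **Group analysis.** "For each group (SCI vs CP), the data will be analyzed as follows". The table beneath has the rows "Greatest change in Ashworth Score vs Location" and "Greatest change in Spasm Rating vs Location", each with an ANOVA entry for SCI and for CP.
- **Selection of subjects.** "We will attempt to enroll ten subjects for each disease category by the end of two years".

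No passage names a primary outcome, ranks the two scores, adjusts for several tests or gives an error rate for the tests taken together.

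**The concern.** A threshold of 0.05 limits the false-positive chance to 5% for one test of one outcome. Here H01 can be rejected by either of two scores, so within each group it has two chances of being rejected wrongly. H01 should say which score decides, but it cannot, because the measure it names does not exist in the protocol.

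The pilot aims to determine whether one location has a significant advantage, and it writes the 0.05 threshold into its hypotheses. A chance result on one score in one group of ten could therefore be read as a real location effect. Both scores will be analysed in any case. What remains open until the data are seen is which of them settles H01.

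**Working it through.** **The plan's own figure.** The only figure is the per-test threshold, p < 0.05. One test gives 1 − 0.95 = 5%. There is no overall rate to reproduce.

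**Inputs**
- Threshold per test: 0.05 (Hypotheses; Methods).
- Scores that may count: 2 (Methods; per-subject question 3).
- Groups analysed separately: 2, with 10 subjects each (Selection of subjects; group table).
- ANOVAs of score by location: 2 × 2 = 4 (group table).
- Correlation between the two scores: not given, so a range is assumed. The same rater scores both on the same subjects, which makes a positive correlation likely.

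**Step 1: independent scores.** With k independent tests and no true effect, P(at least one p < 0.05) = 1 − 0.95^k.
- One group, k = 2: 1 − 0.95² = 9.75%.
- Both groups, k = 4: 1 − 0.95⁴ = 18.55%.

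**Step 2: ceiling under any dependence between scores.** Within a group the rate cannot exceed 0.05 + 0.05 = 10%. The groups are different subjects, so treating them as independent gives at most 1 − (1 − 0.10)² = 19% over both.

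**Step 3: correlated scores.** Null data were simulated for a repeated-measures ANOVA with 10 subjects, 4 locations, normal scores and 200,000 runs. With p the either-score rate in one group, the four-ANOVA rate is 1 − (1 − p)².

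| Assumed correlation | Either score, one group | Any of four ANOVAs |
|---|---|---|
| 0 | 9.8% | 18.7% |
| 0.3 | 9.4% | 18.0% |
| 0.5 | 9.3% | 17.7% |
| 0.7 | 8.6% | 16.5% |
| 0.9 | 7.2% | 13.9% |
| 1 (exact) | 5% | 9.75% |

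The row for 0 differs from Step 1 only by simulation error. In the last row the two scores act as one test, so 1 − 0.95² = 9.75% across the groups comes from testing SCI and CP separately. Correlation between scores cannot remove that part.

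**Step 4: one deciding score.** If the Ashworth score alone decides, and the spasm test is read formally only after a significant Ashworth test, the rate within a group is 5%. Across two groups it is 1 − 0.95² = 9.75%.

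**The case against.** **This is a pilot, with no success rule and no promised overall 5%.** This stands. A reader might infer that the protocol declares success if either score is significant, or that it claims an overall 5% and misses it. It does neither. It expresses an interest in significant changes and sets a per-test threshold. The gap is that H01 carries a significance level without a defined outcome.

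**The 10% is a ceiling.** This also stands. The two scores come from the same subjects, sessions and rater, so the actual rate is probably lower. The simulation adds its own assumptions: normal data and a repeated-measures model, where the protocol says only ANOVA and the scores are ordinal, 0 to 4.

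**The trigger for further disease categories is a different test.** A reader might infer that the decision to study other categories carries the same 10% or 19%. It does not. Selection of subjects ties that step to a difference between the two groups, which is the H02 comparison. The four ANOVAs compare locations within a group. The protocol does not say which score the trigger uses or how many tests it involves.

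**Both scores are already committed to, and H01 leans towards Ashworth.** Largely true. The aims, questions and table analyse both, and Methods elsewhere pairs spasticity with the Ashworth score. The merged name may be a slip. But the either/or wording remains, so correcting the name alone would not settle which score decides.

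**SCI and CP are separate questions.** This is defensible, since the protocol predicts different results for them. Adjusting across all four ANOVAs (0.0125 each gives 1 − 0.9875⁴ = 4.91% if independent) is a debatable trade with ten subjects per group, and it is not asked for here.

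**Conclusion.** The point holds as a gap in how H01 is defined and decided. H01 names an outcome that is not defined, and either of two scores may count at an unadjusted 0.05. With no location effect, the chance of at least one false positive is at most about 10% per group and about 19% over the four ANOVAs. At assumed score correlations of 0.3 to 0.9 it is roughly 9.5% down to 7%, and 18% down to 14%.

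These figures assume that each ANOVA keeps its own 5% level and that the groups are independent. They cover only the four location ANOVAs. The H02 comparison and any test of day-to-day differences would come on top, but the protocol does not say how many tests those involve.

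The figures do not show that the actual rate is 10%, because the correlation is unknown. The change is worth making because it replaces an undefined outcome and an explicit either/or with one stated decision.

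**What to change.** 1. **H01.** Replace "as measured by using the Modified Ashworth Spasm Rating Score" with: *as measured by the Modified Ashworth score (Table 2)*.
2. **Methods, first paragraph, and per-subject question 3.** Replace the either/or wording with: *The Modified Ashworth score is the primary outcome and alone decides H01, tested at p < 0.05 within each patient group. The Penn spasm score is secondary. Its test is interpreted formally only in a group where the Ashworth test is significant, and is otherwise descriptive.*
3. **Group analysis.** Add: *This holds the false-positive rate at 5% within each group. Because SCI and CP are tested separately, the chance of at least one false positive across the two groups is up to 9.75%, and results will be reported with that statement.*

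The cost is a few sentences, with no new data, subjects or visits. The downside is that an effect seen only on spasms becomes hypothesis-generating, which is acceptable in a 20-subject pilot.
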